Colorectal Cancer Screening Assessment Study in American Samoa

NCT04500171- American Samoa Community Cancer Coalition and the UH Cancer Center

Background / Statement of Need

Brief Summary.

Colorectal Cancer is the third most prevalent cancer in American Samoa for both men and women. Fortunately, screening modalities such as FOBT, flexible sigmoidoscopy, and colonoscopy are available on island. However, only 7% of eligible adults have reported receiving screening versus 62.9% in the U.S. (ASDOH, 2013¹). Low and/or no participation in preventive health services is associated with knowledge deficits on health promotion behaviors. However, there were no studies to identify contributing knowledge risk factors and colorectal cancer screening within the indigenous Samoan population. In 2018 the Indigenous Samoan Partnership to Initiate Research Excellence (INSPIRE) conducted a pilot study to determine colorectal cancer (CRC) health literacy levels within the adult population 45 years or older in both English and Samoan using the Short-Test of Functional Health Literacy (S-TOFHLA). Results indicate 81% of the Samoan speaking (N=293) and 44% of the English speaking (N=418) participants demonstrated "inadequate" health literacy. Accordingly, these groups are most likely to have difficulty reading, understanding, and interpreting health materials, directions for their health care and most likely to fail to follow prescribed diets or treatment regimens. Therefore, modifications must be made to CRC screening materials in order to enable the appropriate actions and understanding with these persons.

Purpose and Primary Outcomes.

This study, led by the American Samoa Community Cancer Coalition's INdigenous Samoan Partnership to Initiatie Research Excellence (INSPIRE) and the UH Cancer Center's project team including [name], will utilize a community-based and culturally relevant process to assess the uptake of fecal occult blood testing (FOBT) using tailored colorectal cancer patient education materials for those with inadequate health literacy. Our primary outcomes include: 1) process to develop "suitable" and "comprehensible" health promotion materials for populations in English and Samoan with various health literacy levels, 2) commitment to use the FOBT Colocare home kit, and 3) use of a FOBT Colocare home kit.

Study Overview

Readability, Suitability, and Comprehensibility.

Health literacy is defined by the Institute of Medicine as the "degree to which indivdiuals have the capacity to obtain, process, and understand basic health information and services needed to make appropriate health decisions." The s-TOFHLA has been used to determine individual health literacy in the indigenous population in American Samoa by the 2018 INSPIRE pilot study. However, creating an effective health message that meets varying standards of health literacy levels is the next challenge in which this pilot project addresses.

Creating appropriate messaging to initiate a behavior change involves more than readability. The SMOG and Flesch-Kincaid tools determine grade level reading by the number of polysyllabic words in a paragraph or set number of sentences. This is a limitation as it does not take into account factors that comprise a print message including numeric presentation, illustrations, motivators and reader interaction. Realizing this, Doak et al., determined an improved method to assess the efficacy of patient education material (PEM) was the Suitability Assessment of Materials (SAM), and it evaluated 6 categories: content, literacy demand, graphics, layout/typography, learning stimulation and motivation, and cultural appropriateness. Helitzer et al. (2009), added terms to assess reading, calculating and solving problems creating the Suitability and Comprehensibility Assessment of Materials (SAM + CAM). The SAM + CAM is comprised of 22 evaluation items within the 6 original categories. The instrument has been validated using 69 PEMs on cervical cancer care. Thus, all PEM developed for this project will be evaluated using the SAM + CAM.

Evidence-Based Model

The proposed pilot study is a randomized controlled trial utilizing the evidence based program "Against Colorectal Cancer in Our Neighborhoods" (ACCION) for the Latino population in Texas as a guide. The health belief model and social cognitive theory were used as foundational principles to develop an intervention that builds awareness to initiate a CRC screening behavior modification.

The program was administered in two separate counties (El Paso - intervention & Cameron - control) and used convenience smplaing methods. Recruits in the intervention group were randomized into three areas: presentation only, video, only, or presentation plus video. The control group was given the usual CRC screening protocol and no intervention components. Inclusion criteria were those age 50-75, being uninsured, lived in Texas, and being due for CRC screening.

Results of the study show after a six month follow-up 80.5% (n=467) of the intervention group followed screening recommendations versus 17% (n=317) of the control group. It is also notable there were no discernible differences in screening rates between the intervention methods.

Material Development and Project Resources.

Table 1 provides a brief summary of the Patient Education Materials (PEM) and the assessment tools that will be used to determine efficacy. The project staff will use existing original materials developed by the ColoCARE manufacturer and the Centers for Disease Control and Prevention. A brief instructional video will be created to accompany modified materials for the experiment group.

Table 1. Brief Summary of Patient Education Material Development		
Control Group	English Original	Samoan Original
PEM	Assessment Tools	Assessment Tools
Colocare	SAM + CAM	SAM + CAM
Instruction Sheet	SMOG	Cloze Procedure
CDC Colorectal	SAM + CAM	SAM + CAM
cancer screening	SMOG	Cloze Procedure
for life brochure		
Experiment Group	English Modified	Samoan Modified
PEM	Asessment Tools	Assessment Tools
Colocare	SAM + CAM – Superior rating	SAM + CAM – Superior rating
Instruction Sheet	SMOG – 5 th Grade Level	Cloze Procedure
CDC Colorectal	SAM + CAM – Superior rating	SAM + CAM – Superior rating
Cancer Screening	SMOG – 5 th Grade Level	Cloze Procedure
for Life Brochure		
Colocare	Modified SAM + CAM -Superior	Modified SAM + CAM -Superior rating
Instruction Video	rating	

ColoCARE Disposable Fecal Occult Blood Test

The ColoCARE FOBT is cost effective and a simple way to detect presymptomatic bleeding caused by gastrointestinal diseases. Based upon the design of a traditional guiac slide test, the test pad is placed in the toilet after a bowel movement. The pad is treated with chomogen and if blood is detected will turn a blue and/or green color. There is no requirement for lab staff or the handling of stool. Each kit contains three pads, one large test square and two smaller control squares to verify the system is working properly. Participants who are reported as symptomatic will be referred to the Lyndon Baines Johnson Tropical Medical Center (LBJTMC) for immediate follow up by clinical staff.

Translation

The translation of materials will be done in the following process: forward translation, synthesis, back translation, expert committee review and pretesting (Beaton et al., 2000). The Samoan vocabulary can be described as limited compared to English. The same Samoan word, or phrase, may be used to translate from English even if the PEM is revised to lower grade readability. Consideration of the translations between the control and experiment groups will be discussed within the project staff and consulted with the expert committee.

Assessment Tools: SAM + CAM, Samoan-s-TOFHLA, s-TOFHLA, and HINTS

All original and modified PEMs in both languages will be administered by project staff and pre-testing group. Each of the 22 items within the 6 identified categories are given a score of 0 – 2 based upon certain criteria. Total scores are calculated into percentages and 100% to 70% is superior, "69% to 40%" is "adequate", while 39% - 0% is "not suitable". The data gathered on the original materials will be used to develop the modified versions of the PEM. The goal of the modified version is to achieve a rating of "superior". If the current PEM results in a "superior" rating efforts will be made to increase the modified versions to a higher percentage.

The s-TOFHLA and Samoan-s-TOFHLA are timed reading comprehension tests that uses a modified Cloze procedure to measure understanding of the material. Participants read sentences with missing words and circle the letter (either a, b, c, or d) in front of the word they feel would fit the best. Individual results scored on a scale of 0 to 36. Participants are categorized as having "adequate" if the score is 23–36, "marginal" if it is 17–22, and "inadequate" health literacy if the score is 0–16 (Morris et al., 2006). The s-TOFHLA is a reliable and valid instrument. The Samoan-s-TOFHLA has been used in the INSPIRE study, however is currently being piloted tested in another study for validation.

The Health Information National Trends Survey (HINTS) instrument was developed by the National Cancer Institute to monitor differential dynamics of communication in various cultural contexts to enhance communication strategies and messages effecting health behaviors. The instrument is capable of collecting data on over 23 cancer and health related topics. Our administration of HINTS will include items relevant towards improving the cancer prevention practices and health care utilization of the indigenous Samoan population. The topics and items addressed by our use of HINTS will include: 1) Cancer Communications; 2) Cancer Perceptions and Knowledge; 3) Health Communications; 4) Internet Use; 5) Patient Provider Communications; 6) Risk Perceptions; 7) Social Networks; 8) Tobacco Use; 9) Health Services; 10) Health Status.

Simple Measure of Gobbledygook (SMOG)

The SMOG is a readability assessment tool that uses a formula to calulate grade levels by the number of sentences, total number of words in the sentences, and the number of polysyllabic words. The SMOG has been identified as reliable by the Centers for Medicare and Medicaid Services and considered a more appropriate metric for health materials. The Joint Commission has recommended PEM is written at no higher then a 5th grade level for facilities

seeking accreditation. However, the SMOG is not reliable to determine grade level of PEM translated into non-English languages. Thus, SMOG will be used to determine the grade readability and number of polysyllabic words within the original English PEM. The goal will be to modify the PEM for the experiment group to meet the Joint Commission's recommendation. The modified PEM will be translated for use in the experiment group.

Contextual Measure

There is no known literature to determine the readability of the Samoan language. However, previous studies identify the cloze procedure, used in the s-TOFHLA, as a method to determine contextual meaning. The use of a passage with missing text relies on the reader's "redundancy utilization" or the knowledge of vocabulary, linguistic conventions, and general knowledge. This allows for the reader to predict the context of the passage and is consistent with the natural reading process. For this reason, all translated materials will be pretested using a cloze procedure. Briefly, passages from the PEM will be provided to an individual who meets the eligibility criteria. The PEM will have deleted words replaced by a blank line from the passage in regular intervals. Under each blank line, the test taker will select one out of four options that will complete the passage. The total score will reveal to the project staff if the translation is contextually understood.

Sampling and Recruitment

Program Sites.

Project development, study recruitment and other related activities will take place at the American Samoa Community Cancer Coalition's office in the village of Nu'uuli. Centrally located, it is currently operating two separate studies utilizing RDS. The use of a central point for the study and incentive payment makes it easier for participants to find.

Recruitment of Participants.

To recruit a final sample of 312 participants (English n=156, Samoan n=156), the project staff will initially recruit 24 participants as RDS seeds (12 men and 12 women; 12 English and 12 Samoan). Seeds will be required to meet eligibility requirements and known to have substantial social networks within the community. These seeds will then each recruit a maximum of 3 additional community members. This recruitment pattern will continue to create 3 consecutive recruitment waves (Wave 1, n=24; Wave 2, n=72; Wave 3, n=216). This model will rely on the social networks of the paritipant to recruit and has been successful in the INSPIRE study that recruited 718 participants in 51 days.

Participant Recruitment and Eligibility.

Participants will be eligible if they: 1) are a resident of AS; 2) over age 50; 3) have not been diagnosed or treated for colon cancer; 4) are not high risk for CRC by having family history or diagnosed with irritable bowel syndrome; 5) can read and speak English and Samoan; 5) can provide written informed consent; 6) have a home address and working phone; and 7) are willing to provide information on their health behaviors. Exclusion criteria include persons who indicate they speak or read and write Samoan or English less than well.

Intervention Participation

Participants will be divided into English and Samoan subgroups based upon their RDS recruitment and language preference. Next, participants will take the Samoan-s-TOFHLA or the s-TOFHLA, and the Heatlth Information National Trends Survey (HINTS). Then, participants will be randomized into the control or experiment group (figure 1). Participants in the control group

will receive a ColoCARE FOBT, ColoCARE Instruction Sheet, and the Centers for Disease Control and Prevention's "Colorectal Cancer Screening Saves Lives" brochure in English and Samoan. Participants selected in the experiment group will receive a ColoCARE FOBT, modified ColoCARE Instruction Sheet, ColoCARE instructional video, and a modified CDC "Colorectal Cancer Screening Saves Lives" brochure in English and Samoan. The results will be reported to study staff by phone or in-person at the study center for data entry.

Participants will be given a two week time period to complete the ColoCARE kit, report findings to program staff and recruit 3 additional participants. Participants will receive \$10 during the initial intake screening and completion of the required assessments, \$30 upon report of the ColoCARE results to study staff, and and additional \$15 for each recruit who participates. The total possible incentive for each participant is \$85. This tiered compensation plan is designed to address the increased burden on participants and reduce drop-out by incentivizing continued participation in the study.

[figure not shown]

Figure 1. Project Flowchart

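### The referral rule is triggered by being symptomatic, but the kit looks for bleeding before symptoms and participants report kit results

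*Protocol*

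**What the plan says.** The section ColoCARE Disposable Fecal Occult Blood Test introduces the kit as "a simple way to detect presymptomatic bleeding caused by gastrointestinal diseases". It explains that the treated pad, "if blood is detected will turn a blue and/or green color", and that no laboratory staff are needed. The paragraph closes with the referral rule: "Participants who are reported as symptomatic will be referred" to the local hospital for immediate clinical follow-up.

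Intervention Participation then describes what comes back to the study, in three places:

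- On the route: "The results will be reported to study staff by phone or in-person at the study center for data entry".
- On the two-week period, in which participants are "to complete the ColoCARE kit, report findings to program staff and recruit 3 additional participants".
- On payment: the $30 instalment is due "upon report of the ColoCARE results to study staff".

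**The concern.** The rule uses a clinical state as its trigger, and that state is the opposite of the one the kit is said to detect. Followed as written, it leaves out the symptom-free participant whose pad changes colour.

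This is a working instruction. The kit is used at home without laboratory staff, so the participant reads the pad, and the report by phone or in person is the described point at which staff learn the result. What staff do next depends on this sentence. Relying on participants to seek care unprompted would be a weak safeguard here. The Brief Summary reports inadequate health literacy in 81% of Samoan-speaking and 44% of English-speaking pilot participants, and expects such groups to struggle with directions about their care.

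What is at stake is follow-up of a positive screening test. The randomised comparison and the kit-use outcome do not depend on this sentence.

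**Working it through.** The plan gives no figure to reproduce. The check sets the relevant statements side by side.

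**1. Trigger against purpose.** The first sentence of the kit paragraph uses *presymptomatic* in its ordinary clinical sense. The last sentence of that paragraph uses *symptomatic* as the referral trigger. These are the only two words built on *symptom* in the text available, and the protocol nowhere defines *symptomatic* as a positive test. The word *positive* does not appear.

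**2. Trigger against what is reported.**

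| Statement in Intervention Participation | Kit result? | Symptoms? |
|---|---|---|
| Results reported by phone or in person | yes | no |
| Findings reported within two weeks | yes | no |
| Payment on report of ColoCARE results | yes | no |
| Total | 3 of 3 | 0 of 3 |

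The one purpose stated for these reports is data entry. No sentence available ties a colour change to referral.

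**3. Who is referred under each reading.**

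| Colour change | Symptoms | Rule as written | Probable intent (test positive) | Proposed rule |
|---|---|---|---|---|
| yes | no | not referred | referred | referred |
| yes | yes | referred | referred | referred |
| no | yes | referred | not by this rule | referred |
| no | no | not referred | not referred | not referred |

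The first row is the gap: a participant who needs follow-up because of the kit is not covered by the literal rule.

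**4. Reach.** Recruitment of Participants plans 24 + 72 + 216 = 312 people, and Intervention Participation gives a kit to both arms. The sentence therefore applies to all 312. That is the number under the rule, not the number harmed. The number harmed would be the symptom-free participants with a positive kit whom staff handle literally, and the protocol gives no rate from which to estimate it.

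**The case against.** The strongest reply is that context already settles the meaning. The sentence closes the kit paragraph, just after the colour change and the control squares. If staff receive only kit results, then the only thing that can be reported as symptomatic is a kit result, and on the literal reading the rule would have almost no input. A study team running a screening trial would hardly ignore a reported blue pad because of one word. A result pathway may also appear in Figure 1, on the consent pages or in the ColoCARE instruction sheet, none of which was available for this review. On this view the point is a minor wording correction, and a fix that keeps a symptom trigger treats a slip as intended content.

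Much of this stands. A positive test is probably what was meant, nothing shows that staff would act otherwise, and a pathway elsewhere could remove the practical harm. It cannot be claimed that the trial has no other referral rule. Mentioning data entry does not exclude referral either.

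What does not follow is that the sentence may stay. A safety rule should not depend on readers replacing its key term, least of all when the same paragraph uses the related term in its usual sense. If a correct pathway exists elsewhere, this sentence conflicts with it and still needs correction. Keeping symptoms as an added trigger does no harm and preserves what the rule now literally says.

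**Conclusion.** The concern holds. As worded, the only referral rule in the text available omits the symptom-free participant with a positive kit, and its trigger differs from what participants are asked to report. The sentence should be corrected.

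The size is limited in three ways. No count of affected participants can be given. The harm arises only if staff apply the rule literally and no other pathway overrides it. The trial's estimates are not touched. Confidence is high about what the sentence says; whether anyone would in fact be missed is unknown.

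**What to change.** Replace the last sentence of the kit paragraph with: *Any participant who reports a blue or green colour on the test square is referred to the hospital for immediate follow-up, with or without symptoms; participants who report symptoms are also referred.*

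Naming the test square matters because the kit also contains control squares. The final clause keeps the present rule for symptoms. If the sponsor never intended a symptom rule, replacing *symptomatic* with a positive kit result would close the gap on its own. If Figure 1 or the consent form describes a result pathway, the wording should be made to agree with it.

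The cost is one sentence, with possibly a few more referrals, some for false positives. Sample size, randomisation and outcome definitions stay as they are.

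### Eligibility does not ask whether a participant is due for colorectal cancer screening, so people already up to date enter a trial of FOBT uptake and dilute its arm difference

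*Protocol*

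**What the plan says.** Under Participant Recruitment and Eligibility, the protocol opens its list with "Participants will be eligible if they: 1) are a resident of AS; 2) over age 50". The rest covers no colon cancer, no high-risk status, language, consent, a home address and phone, and willingness to give health information. The exclusion rule concerns language alone: "Exclusion criteria include persons who indicate they speak or read and write Samoan or English less than well". Neither asks whether a person has been screened, or is due.

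Evidence-Based Model names the Texas ACCION programme as the guide and gives its entry rules: "Inclusion criteria were those age 50-75, being uninsured, lived in Texas, and being due for CRC screening".

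Purpose and Primary Outcomes states the aim as assessing FOBT uptake. Two of its three primary outcomes are "2) commitment to use the FOBT Colocare home kit, and 3) use of a FOBT Colocare home kit". The Brief Summary says that FOBT, sigmoidoscopy and colonoscopy can all be had on the island, and that "only 7% of eligible adults have reported receiving screening".

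**The concern.** The trial is motivated by low screening participation and measured by use of a screening kit. As the criteria stand, someone recently screened by any of the locally available methods can enrol, be randomised, receive a kit and count in the denominator.

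If that person leaves the kit unused, the record looks the same as that of someone who is due and declines. If that person uses it, perhaps because reporting a result earns $30, the record shows uptake although no screening gap was closed. Two things are at stake:

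- the size of the arm difference, if the modified materials cannot move people who have no need of the test;
- what a reported uptake percentage describes, and whether it can be set beside the Texas results, which came from people who were due.

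**Working it through.** **Inputs from the protocol**
- Sample size 312, built from recruitment waves (Recruitment of Participants).
- Reported screening 7% (Brief Summary, source dated 2013).
- Texas programme results 80.5% versus 17% (Evidence-Based Model).

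**Inputs assumed, because the protocol does not state them**
- 1:1 allocation, so 312 / 2 = 156 per arm.
- Two-sided 5% test and independent participants.
- The kit-use rates in the illustrations below.
- No effect of the modified materials in people already screened.

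**The plan's own figure.** 24 + (24 × 3 = 72) + (72 × 3 = 216) = 312. It reproduces. It is recruitment arithmetic, with no target effect behind it.

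**People affected.** 0.07 × 312 = 21.8, about 22, or about 11 per arm. The 7% covers everyone who reported screening, and some of them may be due again. So 22 is an approximate upper count of those not due, at that rate.

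**Dilution.** Let f be the share already up to date, with the same kit use q in both arms. Each arm's rate is (1 − f) × p + f × q. The q terms cancel in the difference:

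observed difference = (1 − f) × (p₂ − p₁).

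At f = 0.07 the factor is 0.93. If the materials do raise kit use in this group, the shrinkage is smaller.

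**Power.** Usual normal approximation for two proportions, n = 156 per arm, pooled variance under the null:

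power = Φ{ [d√n − 1.96 √(2p̄(1 − p̄))] / √(p₁(1 − p₁) + p₂(1 − p₂)) }.

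| Assumed rates among those due | Share already screened | Difference (points) | Power |
|---|---|---|---|
| 50% vs 65.6% | 0 | 15.6 | 80% |
| 50% vs 65.6% | 7% | 0.93 × 15.6 = 14.5 | 74% |
| 50% vs 65.6% | 20% (assumption) | 0.80 × 15.6 = 12.5 | 60% |
| 50% vs 70% | 0 | 20.0 | 95% |
| 50% vs 70% | 7% | 0.93 × 20 = 18.6 | 92% |
| 17% vs 80.5% (Texas programme) | 0 | 63.5 | near 100% |
| 17% vs 80.5% | 7% | 0.93 × 63.5 = 59.1 | near 100% |

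The table sets q equal to the control rate. With q = 0, the 74% and 92% figures fall by less than one point, and the 60% figure is unchanged after rounding.

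**Recruitment if a criterion is added.** 312 / (1 − 0.07) = 335.5, so about 336 otherwise eligible people.

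**The case against.** The case for leaving the criteria alone has several sound parts.

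- **The outcome is defined for everyone.** Every participant receives a kit and is asked to report within two weeks. A reader might infer that the uptake outcome does not apply to people already screened. The protocol does not support that: the outcome is use of the supplied kit, which they too can use. Only its reading as uptake among people in need is blurred.
- **No bias between arms.** Screening status precedes randomisation and balances on average.
- **The power loss is illustrative.** The protocol gives no target effect, control rate, error level or allocation ratio. The 15.6-point example sits where 156 per arm gives 80%, so any dilution shows. At larger effects it hardly does. The Texas figures are a different and larger contrast, so they are not a forecast for this trial either.
- **A higher screened share is speculation.** A reader might infer that well-connected seeds recruited by a cancer coalition will bring in more screened people. The protocol says only that seeds must be eligible and have substantial networks. The 20% row has no source in it.
- **A guide is not a template.** The trial also omits the Texas programme's upper age limit and insurance condition. Departing from the guide is no error in itself, and a broad community sample is defensible in a pilot.

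One part is unproven. HINTS is given before randomisation and covers health services, so screening history might be collected. The protocol does not say that it will be. An analysis plan not shown here could report results by screening status, but only if status is recorded, and it cannot change who is enrolled.

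**Conclusion.** The omission is real and the point holds in a modest form. The programme used as guide required "being due for CRC screening"; this trial, whose purpose is FOBT uptake, does not, and gives no reason. The consequence is dilution and an unclear target population. The comparison between arms stays valid.

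At the protocol's own 7%, about 22 of 312 participants are affected, and the observed difference is no smaller than 0.93 of the difference among those due. That bound assumes that the materials do not reduce kit use in the already screened, and that the 2013 figure fits the people recruited. A larger already-screened share is possible but is an assumption. The loss of power runs from negligible to about six points across the effects tried at 7%. A claim that the trial loses substantial power would go beyond what the protocol supports. This is a cheap improvement to the design.

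**What to change.** Add one self-report question on screening history at intake, and an inclusion criterion that the participant is due for colorectal cancer screening. The sponsor should define due, including which tests count and over what period.

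If the sponsor prefers a broad sample, the minimum is to record screening status before randomisation, say so in the protocol, and report kit use among those due beside the result for all participants. This keeps every recruit and makes the uptake figure interpretable. It cannot be added after enrolment if status was never collected.

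The criterion costs one question and, at 7%, about 336 otherwise eligible people approached to enrol 312, some 24 more. The wave plan has no slack for this: it reaches 312 only if every participant in the first two waves brings in three others, so recruits who are turned away would have to be replaced.

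### Participants are paid to recruit acquaintances while holding their arm's materials, and nothing in the protocol text limits sharing; at 1:1 with full waves, about 46% of controls would have an experiment-arm recruiter

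*Protocol*

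**What the plan says.** Under Recruitment of Participants, the sample is built by respondent-driven sampling from 24 seeds. "These seeds will then each recruit a maximum of 3 additional community members", and the pattern continues to give "Wave 1, n=24; Wave 2, n=72; Wave 3, n=216", a total of 312. The protocol states that "This model will rely on the social networks of the paritipant to recruit", so recruiter and recruit are expected to know each other.

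Under Intervention Participation, after the language split and the baseline instruments, "Then, participants will be randomized into the control or experiment group". No cluster, recruitment chain or recruiter is named as the unit of allocation. Controls receive the kit with the unmodified instruction sheet and brochure. For the other arm, "Participants selected in the experiment group will receive a ColoCARE FOBT, modified ColoCARE Instruction Sheet, ColoCARE instructional video" and a modified brochure. Every participant then has two weeks to "complete the ColoCARE kit, report findings to program staff and recruit 3 additional participants", with a payment of $15 "for each recruit who participates".

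Purpose and Primary Outcomes lists among the primary outcomes "commitment to use the FOBT Colocare home kit, and 3) use of a FOBT Colocare home kit".

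The text does not ask participants to keep their materials from the people they recruit, or from whoever recruited them. It does not say whether the video is taken home.

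**The concern.** The recruiting task falls in the same two weeks in which a participant holds the arm's materials, and it sends that participant to acquaintances who are then randomised separately. A recruiter usually enrols before the recruit, so the modified sheet, brochure or video could reach a future control before that person uses the kit, or even before baseline. The language split is no barrier: Participant Recruitment and Eligibility requires participants to read and speak both languages.

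The materials are the only difference between the arms. If controls are exposed to the modified versions and experiment-arm recruits gain nothing extra from the same exposure, the arm difference in kit use and commitment narrows, and effective materials could look less effective than they are. If both arms gain equally, the difference does not change. No analysis can undo exposure that has already happened, so the place to limit it is the conduct of the trial.

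**Working it through.** **Inputs from the protocol**
- Seeds: 24; recruits per participant: at most 3; waves: 24, 72, 216 (Recruitment of Participants).
- Allocation by participant (Intervention Participation).

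**Assumptions, not in the text**
- Allocation ratio 1:1. Arm sizes of 156 follow from this; the 156 printed in the protocol is per language.
- All waves fill.
- Figure 1 was not available.

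**Step 1. Reproduce the protocol's total.** 24 + 24×3 + 24×9 = 24 + 72 + 216 = 312, as stated. By language, 12 + 36 + 108 = 156, also as stated.

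**Step 2. Participants who have a participant recruiter.** All but the seeds: 312 − 24 = 288, and 288/312 = 92.3%.

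**Step 3. Controls with an experiment-arm recruiter.** Each non-seed has one recruiter, who is in the experiment arm with probability 0.5:

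0.923 × 0.5 = 0.4615, that is 72 of 156.

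With exactly 156 per arm, the figure is 0.923 × 156/311 = 46.3%. Simulating allocation on the 24 → 72 → 216 tree gives a central 95% range of about 35% to 58% with simple randomisation, and 36% to 56% with exactly 156 per arm. These ranges reflect chance in allocation only.

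**Step 4. Vary the assumptions.**

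| Assumption | Controls with an experiment-arm recruiter |
|---|---|
| 1:1, full waves (N = 312) | 46% |
| 1:2 experiment:control | 0.923 × 1/3 = 31% |
| 2:1 experiment:control | 0.923 × 2/3 = 62% |
| 1:1, two recruits each (N = 24+48+96 = 168) | 144/168 × 0.5 = 43% |
| 1:1, one recruit each (N = 24+24+24 = 72) | 48/72 × 0.5 = 33% |

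**Step 5. Links in both directions.** The chance of at least one experiment-arm recruiter or recruit is:
- seeds: 1 − 0.5³ = 0.875
- Wave 2: 1 − 0.5⁴ = 0.9375
- Wave 3: 0.5

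(24×0.875 + 72×0.9375 + 216×0.5)/312 = 196.5/312 = 63% (simulated range 54% to 72%). The recruit-to-recruiter direction matters only if the control has not yet used the kit, so 63% is a looser figure than 46%.

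**Step 6. Possible effect on the result.** Let a fraction c of the controls in Step 3 respond as if in the experiment arm, with no extra gain for experiment-arm recruits. The control rate moves toward the experiment rate by 0.4615c of the gap, so the observed difference is the true difference × (1 − 0.4615c).
- c = 0.25: 12% smaller
- c = 0.5: 23% smaller
- c = 1 (bound): 46% smaller

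The protocol gives no information on c.

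**The case against.** The strongest reply is that this is an omission, not a misstatement. One line telling participants not to share could sit in a consent form or a staff script; the consent pages were not available here, so its absence from the protocol text does not prove that participants were told nothing. The ratio is assumed, and Figure 1 might show a different ratio or allocation by chain. The 46% follows for any 1:1 individually randomised trial recruited this way; it does not show that a recruiter shows the leaflet to a recruit, that this happens before kit use, or that it changes behaviour. The shrinkage figures are an adverse case, the bias would be toward no difference, and the protocol calls the study a pilot. Nor can an instruction be enforced or stop acquaintances talking about the kit.

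Much of this stands as a limit on size. The sharing rate is unknown, the ratio matters, and the route can be reduced but not closed. It does not remove the point. The unit of randomisation, the handling of arm materials and the timing of recruitment are design matters, set in this protocol, and together they create the exposure route. The consent form is only a possible location for a safeguard. The link between arms remains substantial across the assumptions tried: 31% to 62% over the allocation ratios, and 33% with one recruit each.

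**Conclusion.** The concern holds. As written, the design pays participants to approach acquaintances while they hold arm-specific materials, randomises those acquaintances individually, and states no limit on sharing. With 1:1 individual randomisation and full waves, about 46% of controls would have an experiment-arm recruiter. This is opportunity, not measured contamination. Loss of effect depends on an unknown sharing rate and on experiment-arm recruits not gaining equally from the same exposure. Confidence is medium because Figure 1 and the consent pages could not be seen. The change should be made: the outcomes at risk are primary, and the safeguard is cheap.

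**What to change.** In Intervention Participation, add an instruction given at hand-out in both arms. Participants may describe the study in order to recruit, but should not show or pass on their instruction sheet, brochure or video to people they recruit, or to whoever recruited them, until those people have reported their own result or their two weeks have ended. If the consent form or a staff script already says this, the protocol should state it too.

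Keep the recruiter-to-recruit link, which the $15 payment already requires, in the trial dataset so that kit use can be described by recruiter's arm. Label that summary supportive and descriptive; it cannot exclude contamination.

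The cost is one instruction and retention of existing information, with no new visits, participants or tests. The instruction may be imperfectly followed, does not cover two people who share a recruiter, and briefly delays informal sharing of the materials among participants.
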